2.9 Patient-reported outcomes

This study is a single arm study. Therefore, the PRO analyses will be descriptive and no statistical models will be provided.

The EQ-5D-5L is a general health status and health utility measure ([Rabin 2001](#)) and measures 5 dimension of health state: mobility, self-care, usual activities, pain/discomfort, and anxiety/depression each assessed by a single question on a five-point ordinal scale EQ-5D Visual Analog Scale (VAS) is also included. The FKSI-Disease Related Symptoms (FKSI-DRS) is a 9-item questionnaire specifically designed to evaluate symptoms that are directly attributable to kidney cancer ([Cella 2007](#)) and includes patient's symptoms in the past seven days such as lack of energy, pain, bone-pain, shortness of breath, fatigue, blood in urine, etc. The scoring of these instruments will be done in accordance with the respective user's manual of the instrument.

Handling of missing data and generation of standard scores for the analysis will be performed in accordance with the respective scoring manual.

The FAS will be used for analyzing PRO data unless specified differently.

The PRO instruments are planned to be administered during screening and every 4 weeks after first day of treatment during the first 6 months, every 8 weeks thereafter until the first 11 months and then every 12 weeks until the end of treatment.

The baseline is defined as the last PRO assessment on or prior to first day of treatment. Distribution of patients on the 5 dimensions by level of problem at each schedule visit for EQ-5D-5L will be tabulated. The VAS scores from the EQ-5D-5L and FKSI-DRS will be displayed as mean profiles, presented over time using time windows as described in [Table 2.1](#). Change from baseline scores at the time of each assessment will also be summarized on patients with an evaluable baseline score and at least one evaluable post baseline score during the treatment period.

Compliance to the schedule of administration of PRO will be summarized, for baseline and post-baseline on treatment assessments points. The following categories, as collected on the eCRF, will be used to describe whether the questionnaire was completed at a specific time point:

1. yes, fully completed
2. yes, partly completed
3. no, other.

[REDACTED]

2.11 Other Exploratory analyses

Karnofsky Performance Scale

The Karnofsky performance score (KPS) allows patients to be classified as to their functional impairment. The score runs from 100 down to 0, where 100 is "perfect" health and 0 is death. The definition of scores in relation to the performance status is given in [Table 2-8](#).

Table 2-8 Karnofsky Performance Scale

Score	Performance Status
100	Normal: no complaints, no evidence of disease
90	Able to carry on normal activity; minor symptoms
80	Normal activity with effort; some symptoms
70	Cares for self; unable to carry on normal activities
60	Requires occasional assistance; cares for most needs
50	Requires considerable assistance and frequent care
40	Disabled: requires special care and assistance
30	Severely disabled: hospitalized but death not imminent
20	Very sick: active supportive care needed
10	Moribund: fatal processes are progressing rapidly
0	Dead

All collected data will be presented in data listings.

Duration of follow-up

Study follow-up will be summarized using the following methods:

- Summary of duration between start date of treatment and cut-off date, and follow-up times for PFS/OS, which are defined as follows:
 - Duration between start date of treatment and data cut-off date = (Cut-off date – Date of start of treatment + 1) / 30.4375 (months). This item will be summarized overall.
 - Follow-up time = (Date of event or censoring – Date of start of treatment + 1) / 30.4375 (months) regardless of censoring. Date of censoring is defined as the last adequate tumor assessment date for PFS or last contact date for OS. This item will be summarized.

All summaries will be reported in months. The calculations for PFS will be based on local assessment. Date of censoring is the same as defined for the PFS and OS analysis.

2.12 Interim analysis

No formal interim analysis is planned for this trial.

3 Sample size calculation

3.1 Primary analysis

Single arm study with PFS as primary endpoint

Since there is no formal hypothesis testing, sample size for this study is not based on any statistical power consideration. A total of approximately 100 patients (with approximately 40 patients receiving pazopanib as 2nd-line therapy) are planned to be enrolled and treated in this study. In a retrospective study, Nadal et al. reported median PFS (mPFS) of 6.9 months (95% CI: 3.7 to 10.1) in mRCC patients treated with VEGFR-TKI therapy after any PD-1 combination

([Nadal et al 2016](#)). Based on this data, the median PFS for this patient population treated with pazopanib following prior treatment with immune checkpoint inhibitors is assumed approximately 6 months or less. Considering a recruitment period of 12 months and 6 months of follow up after LPFV, the expected 95% CIs for a median PFS for overall, 2nd line, and 3rd line patients with different sample sizes are presented in [Table 3-1](#).

Table 3-1 Sample size and estimated 95% CI for median PFS

Patient population	Median PFS	Sample size	95%CI of median	Width (months)
			PFS (month)	
Overall	5 months	90	3.96, 6.31 2.35	3.96, 6.31 2.35
		100	4.01, 6.24 2.23	4.01, 6.24 2.23
		110	4.05, 6.17 2.12	4.05, 6.17 2.12
2 nd line	6 months	30	3.95, 9.12 5.18	3.95, 9.12 5.18
		40	4.17, 8.62 4.45	4.17, 8.62 4.45
		50	4.34, 8.30 3.96	4.34, 8.30 3.96
3 rd line	4 months	50	2.96, 5.40 2.44	2.96, 5.40 2.44
		60	3.04, 5.26 2.22	3.04, 5.26 2.22
		70	3.10, 5.16 2.05	3.10, 5.16 2.05

3.2 Power for analysis of key secondary variables

Not applicable.

4 Change to protocol specified analyses

To follow the Novartis standard, prior, concomitant and post therapies will be provided on the Full Analysis Set instead of the Safety Set as per protocol.

Per Protocol Set (PPS) was defined in the original protocol, however, analysis by PPS population (including PPS definition) will not be conducted due to the fact that (i) sample size reduction and (ii) SAP leaning principal.

AESI main risk names were updated according to the last CRS available at the time of the SAP finalization.

5 Appendix

5.1 Imputation rules

5.1.1 Study drug

The following rule should be used for the imputation of the dose end date for a given study treatment component:

Scenario 1: If the dose end date is completely missing and there is no EOT page and no death date, the patient is considered as on-going:

The patient should be treated as on-going and the cut-off date should be used as the dose end date.

Scenario 1 should not applicable for final CSR. All patients should have EOT page complete before the Database lock for Final CSR.

Scenario 2: If the dose end date is completely or partially missing and the EOT page is available:

Case 1: The dose end date is completely missing, and the EOT completion date is complete, then this latter date should be used.

Case 2: Only Year(yyyy) of the dose end date is available and yyyy < the year of EOT date:

Use Dec31yyyy

Case 3: Only Year(yyyy) of the dose end date is available and yyyy = the year of EOT date:

Use EOT date

Case 4: Both Year(yyyy) and Month (mm) are available for dose end date, and yyyy = the year of EOT date and mm < the month of EOT date:

Use last day of the Month (mm)

All other cases should be considered as a data issue and the statistician should contact the data manager of the study.

After imputation, compare the imputed date with start date of treatment, if the imputed date is < start date of treatment:

Use the treatment start date

Patients with missing start dates are to be considered missing for all study treatment component related calculations and no imputation will be made. If start date is missing then end-date should not be imputed.

5.1.2 AE, ConMeds and safety assessment date imputation

Table 5-1 Imputation of start dates (AE, CM) and assessments (LB, EG, VS)

Missing Element	Rule
day, month, and year	
• No imputation will be done for completely missing dates
day, month	
• If available year = year of study treatment start date then
◦ If stop date contains a full date and stop date is earlier than study treatment start date then set start date = 01JanYYYY
◦ Else set start date = study treatment start date.• If available year > year of study treatment start date then 01JanYYYY• If available year < year of study treatment start date then 01JulYYYY
day	
• If available month and year = month and year of study treatment start date then
◦ If stop date contains a full date and stop date is earlier than study treatment start date then set start date= 01MONYYYY.
◦ Else set start date = study treatment start date.• If available month and year > month and year of study treatment start date then 01MONYYYY• If available month and year < month year of study treatment start date then 15MONYYYY

Table 5-2 Imputation of end dates (AE, CM)

Missing Element	Rule (*=last treatment date plus 30 days not > (death date, cut-off date, withdrawal of consent date))
day, month, and year	
• Completely missing end dates (incl. ongoing events) will be imputed by the end date of the on-treatment period*
day, month	
• If partial end date contains year only, set end date = earliest of 31DecYYYY or end date of the on-treatment period *
day	
• If partial end date contains month and year, set end date = earliest of last day of the month or end date of the on-treatment period*

Any AEs and ConMeds with partial/missing dates will be displayed as such in the data listings.

Any AEs and ConMeds which are continuing as per data cut-off will be shown as 'ongoing' rather than the end date provided.

The above imputations are only used for analyses of time to and duration of AEs and concomitant medications.

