4. Action taken with respect to study treatment (none, dose adjusted, temporarily interrupted, permanently discontinued, unknown, not applicable)
5. Whether medication or therapy was given (no concomitant medication/non-drug therapy, concomitant medication/non-drug therapy)
6. Whether it is serious, where a serious adverse event (SAE) is defined as in [Section 8.2.1](#) and which seriousness criteria have been met

7. Outcome (not recovered/not resolved, recovered/resolved, recovering/resolving, recovered/resolved with sequelae, fatal, unknown)

If the event worsens the event should be reported a second time in the CRF noting the start date when the event worsens in toxicity. For grade 3 and 4 adverse events only, if improvement to a lower grade is determined a new entry for this event should be reported in the CRF noting the start date when the event improved from having been Grade 3 or Grade 4.

All adverse events should be treated appropriately. If a concomitant medication or non-drug therapy is given, this action should be recorded on the Adverse Event CRF.

Once an adverse event is detected, it should be followed until its resolution or until it is judged to be permanent, and assessment should be made at each visit (or more frequently, if necessary) of any changes in severity, the suspected relationship to the study treatment, the interventions required to treat it, and the outcome.

Progression of malignancy (including fatal outcomes), if documented by use of appropriate method (i.e. as per RECIST criteria), should not be reported as a serious adverse event.

Adverse events separate from the progression of malignancy (example, deep vein thrombosis at the time of progression or hemoptysis concurrent with finding of disease progression) will be reported as per usual guidelines used for such events with proper attribution regarding relatedness to the drug.

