10.5.3 Safety objectives

10.5.3.1 Analysis set and grouping for the analyses

For all safety analyses, the safety set will be used. Summary table and patient data listings will be used to analyze and present safety data.

The overall observation period will be divided into three mutually exclusive segments:

1. pre-treatment period: from day of patient's informed consent to the day before first dose of study medication;
2. on-treatment including safety follow-up period: from day of first dose of study medication to 30 days after last dose of study medication;
3. post-treatment period: starting at day 31 after last dose of study medication.

If dates are incomplete in a way that clear assignment to pre-, on-, post-treatment period cannot be made, then the respective data will be assigned to the on-treatment period.

For the safety evaluations (with the exception of AEs), the last available assessment performed on or before the date of study treatment start will be considered as the "baseline" assessment.

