10.5.3.2 Adverse events (AEs)

Summary tables for adverse events (AEs) will include only AEs that started or worsened during the on-treatment period, the **treatment-emergent** AEs.

The incidence of treatment-emergent adverse events (new or worsening from baseline) will be summarized by system organ class and or preferred term, severity (based on NCI-CTCAE grades), relation to study treatment.

Serious adverse events, non-serious adverse events, adverse events of special interest (AESI) (see [Section 8.1.3](#)) and adverse events leading to study treatment discontinuation during the on-treatment period will be tabulated for safety set as well as by line of therapy subgroup (2nd/3rd), age category and MSKCC and IMDC risk groups.

All deaths (on-treatment and post-treatment) will be summarized.

All AEs, deaths and serious adverse events (including those from the pre and post-treatment periods) will be listed and those collected during the pre-treatment and post-treatment period will be flagged.

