2. **on-treatment period:** from date of first administration of study treatment to 30 days after date of last actual administration of any study treatment (including start and stop date)
3. **post-treatment period:** starting at day 30+1 after last administration of study treatment.

Safety summaries (tables, figures) include only data from the on-treatment period with the exception of baseline data which will also be summarized where appropriate (e.g. change from baseline summaries). In addition, a separate summary for death including on-treatment and post-treatment deaths will be provided. In particular, summary tables for adverse events (AEs) will summarize only on-treatment events, with a start date during the on-treatment period (**treatment-emergent** AEs).

However, all safety data (including those from the post-treatment period) will be listed and those collected during the pre-treatment and post-treatment period will be flagged.

Windows for multiple assessments of PRO

In order to summarize PRO measures and performance status (PS) collected over time (including unscheduled visits), the assessments will be time slotted. The following general rule will be applied in creating the assessment windows: If more than one assessment is done within the same time window, the assessment performed closest to the target date will be used. If two assessments within a time window are equidistant from the target date, then the worst of the two assessments will be used. If multiple assessments on the same date then the worst case will be used. Data obtained at the end of treatment will be classified as other assessment in the corresponding time window. Data from all assessments (scheduled and unscheduled), including multiple assessments, will be listed.

Note that only data collected under treatment (i.e. while the patient is treated) will be included in the time to definitive deterioration. The end of treatment assessment will be included if collected within 30 days of the last dose intake.

Table 2-1 Time windows for EQ-5D-5L, KPS and FKSI-DRS assessments

Assessment	Target day of	Time Interval
Baseline		≤ Day 1
Cycle 2 Day 1	29	Day 2 to day 42
Cycle 3 Day 1	57	Day 43 to day 70
Cycle 4 Day 1	85	Day 71 to day 98
Cycle 5 Day 1	113	Day 99 to day 126
Cycle 6 Day 1	141	Day 127 to day 154
Cycle 7 Day 1	169	Day 155 to day 196
Cycle 9 Day 1	225	Day 197 to day 252
Cycle 11 Day 1	281	Day 253 to day 308
Cycle 13 Day 1	337	Day 309 to day 378

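### The SAP omits the protocol's rule for AE dates that cannot be placed, and its start-date definition can, rarely, count an improvement-only record as treatment-emergent

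*SAP*

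**What the plan says.** **Protocol.** Section 10.5.3.1 divides observation into pre-, on- and post-treatment periods and adds a rule for poor dates. Where a date does not show which period applies, the instruction is "then the respective data will be assigned to the on-treatment period". Section 10.5.3.2 then says that the AE summary tables "will include only AEs that started or worsened during the on-treatment period". Section 8.1.1 sets how AEs reach the CRF. A worsened event is entered again, dated at worsening. For Grade 3 and 4 events, "if improvement to a lower grade is determined a new entry for this event should be reported in the CRF", dated at the improvement.

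**SAP.** Sections 2.1.1 and 2.8 repeat the three periods without the protocol's rule for incomplete dates. Section 2.1.1 says that the AE tables "will summarize only on-treatment events, with a start date during the on-treatment period". In Section 5.1.2, Table 5-1 imputes partial AE start dates, but for a date missing altogether it states "No imputation will be done for completely missing dates". The section closes with "The above imputations are only used for analyses of time to and duration of AEs and concomitant medications". Sections 2.8.1 and 2.8.1.1 list no time-to or duration analysis of AEs. Section 4, which records departures from the protocol analyses, mentions a change to the AESI risk names but nothing about incomplete AE dates or the definition of treatment-emergent.

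**The concern.** Read together, the SAP sentences define a treatment-emergent AE by start date and keep imputed dates away from that decision. They also leave out the one protocol sentence that would settle the cases where the date does not show the period. A programmer working from the SAP alone has no instruction for an AE dated only to the month of first dose, or with no start date. Comparing the recorded date with the period limits would fail, and the record would not reach the tables. The protocol chose the conservative direction for such records, namely to count them.

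The definition also has a side effect in the other direction. A start-date rule cannot tell a record opened because an event began or worsened from one opened because it improved. A pre-dose Grade 3 or 4 event that only gets better after first dose therefore enters the tables.

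Safety is a named secondary objective of this single-arm trial of about 100 patients, with incidences of AEs, SAEs and AESIs among its outputs.

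**Working it through.** The plan gives no figure to reproduce on this point, so the check applies the rules to examples.

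**1. Incomplete start dates.** Assumed illustrative patient: consent 28 days before first dose (15 Feb 2018), first dose 15 Mar 2018, last dose 10 Oct 2018. On-treatment then runs to 10 Oct + 30 days = 9 Nov 2018. No full stop date before first dose is assumed. The last column shows what Table 5-1 would give if the SAP allowed its use for period assignment.

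| Recorded AE start | Periods it could fall in | Protocol 10.5.3.1 | SAP Table 5-1, if allowed |
|---|---|---|---|
| day unknown, Feb 2018 | pre | pre | 15 Feb 2018: pre |
| day unknown, Mar 2018 | pre, on | **on** | 15 Mar 2018: on |
| day unknown, Jun 2018 | on | on | 1 Jun 2018: on |
| day unknown, Nov 2018 | on, post | **on** | 1 Nov 2018: on |
| day unknown, Dec 2018 | post | post | 1 Dec 2018: post |
| year only, 2018 | pre, on, post | **on** | 15 Mar 2018: on |
| year only, 2019 | post | post | 1 Jan 2019: post |
| completely missing | pre, on, post | **on** | not imputed |

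Four of the eight patterns are clear without any rule (1 pre, 1 on, 2 post). The other four are ambiguous, and the protocol puts all four on-treatment. The SAP as written has no usable rule for these four. Allowing Table 5-1 would settle three of them, but not the completely missing date.

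Table 5-1 is not a full substitute even for partial dates. Take an AE with start year 2018 only and a stop date recorded as February 2018, day unknown. It ended before first dose, so it is clearly pre-treatment. Table 5-1 makes its exception only for a full stop date, so it would set the start to 15 Mar 2018, which is on-treatment.

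**2. Improvement records.** Grade 3 onset on 1 Mar 2018 is pre-treatment. If the event improves to Grade 2 on 1 Apr 2018, Protocol 8.1.1 calls for a second entry with that start date. The SAP start-date rule classes the second entry as on-treatment and counts it at its lower grade, although nothing began or worsened on treatment.

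For an event that began on treatment the problem disappears, because SAP 2.8.1 counts a patient once per category at the maximum grade. Worsening is not lost either, because the worsened event has its own dated entry.

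**3. Size.** The tables count patients, so with N of about 100 one misclassified patient is 1/100 = 1 percentage point of the incidence concerned, provided that the patient has no other on-treatment record in that category. Neither the number of unplaceable dates nor the number of improvement entries is in the documents. If 1 to 5 patients were affected in a category (an assumption), the shift would be 1 to 5 points: downward for unplaced dates, upward for improvement records.

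**The case against.** The strongest reply is that the SAP excludes nothing. It states that it is based on the protocol, Section 4 declares no change here, and so the protocol's rule can be taken as still in force. Section 2.8.1 speaks of AEs occurring in the on-treatment period and flags those that start outside it, and a date known only to the month of first dose has not been shown to lie outside. This stands in part. A reader might infer that every incompletely dated AE is dropped by rule. The documents do not support that: the SAP is silent on these records, their loss is a consequence of literal programming, and only dates too incomplete to place are involved.

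A reader might also infer that dropping the worsening clause loses worsened events. It does not, for the CRF reason shown above.

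Data controls reduce the exposure. Protocol 8.1.1 asks for start and end dates, Section 9.4 requires queries on missing values before lock, and SAP 2.8.1 lists all AEs whatever their period. These make unplaceable dates fewer but give no rule for those that remain.

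The improvement case is narrow. It needs a Grade 3/4 event that arises between consent and first dose, with screening assessments confined to the 28 days before treatment, and that improves on treatment. Conditions already present at consent go to medical history, and unresolved checkpoint-inhibitor toxicity above Grade 1 is an exclusion criterion. That limits how often it happens; the mechanism remains.

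**Conclusion.** The point holds as a gap in the SAP. The protocol's rule for unplaceable dates is missing from it, the omission is not declared, and the limit on imputation leaves those AEs no route into the tables if the text is programmed literally. Separately, the start-date definition admits a rare kind of record that the protocol's definition would not count.

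The size is unknown. Each affected patient is worth about 1 percentage point of an incidence at N of about 100, and the 1 to 5 point range rests on an assumed 1 to 5 patients. The two effects run in opposite directions, so the documents do not support a claim of net under-counting. Nor do they support an estimate of lost AE records: they give no count of such records, and the tables count patients.

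**What to change.** - In SAP 2.1.1 and 2.8, restore the rule of Protocol 10.5.3.1: an AE whose period cannot be clearly assigned, including one with a completely missing start date, is on-treatment.
- In the same place, define treatment-emergent as in Protocol 10.5.3.2, that is, begun or worsened on treatment.
- Link a record opened only because a Grade 3/4 event improved to its original event, so that it does not count as a new one.
- Keep the limiting sentence in SAP 5.1.2 and add that period assignment follows the restored rule. Deleting it would let Table 5-1 decide the period, which misplaces the partial-stop-date case above and still leaves completely missing dates unresolved. It would also widen the imputation for concomitant medications.

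The cost is a few sentences and a linking step in the AE programming. AE counts may change slightly in either direction.
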